10.2. Safety analysis

Data name	Derivation and calculation methods
Adverse event	
The adverse events for analysis should include not only the events derived from the survey form but also the events covered in the detailed investigation which has been described by the physicians at a contracted site/department even though not derived from the survey form in “Humira CD Long_AE matching list”.
 
With adverse event: at least 1 record on adverse event(s) exists Without adverse event: other than the above.
 
When adverse events are counted per SOC, the identical SOC in a patient should be counted as 1 whereas the same PT in the same patient be counted as 1 for PT. When no applicable patients were observed, display “0” for the number of patients and “0.00” for the percentage.

Seriousness of adverse events	
Based on the seriousness criteria for company assessment which are provided in “Humira CD Long_AE matching list”, regard the events which have been assessed to be serious as serious adverse events.
 
With serious adverse event: at least 1 record on serious adverse event(s) exists Without serious adverse event: other than the above.
 
Follow the way of counting adverse events to count serious adverse

Data name	Derivation and calculation methods
	
events.
 
Give the following priority to serious adverse events for aggregation.
 
[1]serious [2]non-serious

Causal relationship of adverse events	
Unless a serious adverse event is assessed as “not related” in the company causality assessment provided in “Humira CD Long_AE matching list”, regard the event as ‘with’ causal relationship. Give the following priority to causal relationship for aggregation.
 
[1] With causal relationship [2] without causal relationship

Outcome of adverse events	
Use the outcomes for company assessment provided in “Humira CD Long_AE matching list” to give the following priority to the outcomes for aggregation based on the rules in “derivation and calculation methods” for adverse events.
 
[1] [1] death [2] unknown [3] not recovered [4] recovered with sequela [5] recovering [6] recovered [7] not provided

Days from the first administration date of Humira to the adverse-event onset date	
Use the onset date for company assessment provided in “Humira CD long-term_AE matching list”.
 
When the first administration date of Humira and the adverse-event onset date can be identified as the complete date, they can be used for calculation.
 
When the first administration date of Humira <= the adverse-event onset date:
 
Adverse-event onset date - the first administration date of Humira + 1
 
When the first administration date of Humira > the adverse-event onset date:
 
Adverse-event onset date - the first administration date of Humira
 
When more than one identical PT is found in a patient, use the first onset date to identify the adverse event to be counted.

Days from the adverse-event onset date to the outcome confirmation date (recovered or recovering)	
Use the onset date and the outcomes (recovered or recovering) for company assessment provided in “Humira CD Long_AE matching list”.
 
When the adverse-event onset date and the outcome confirmation date can be identified as the complete date, they can be used for calculation.
 
Outcome confirmation date - adverse-event onset date + 1
 
When more than one identical PT is found in a patient, choose the event which persisted longest until the recovery or the outcome confirmation date.

Data name	Derivation and calculation methods
Incidence of adverse reactions, incidence of serious adverse reactions, incidence of adverse events, incidence of serious adverse events	
Calculate the incidence of adverse reactions, incidence of serious adverse reactions, incidence of adverse events, incidence of serious adverse events with the number of patients with any of the reactions/events in numerator and the number of patients in the safety analysis group in denominator.
 
Provide how to calculate in each table at Chapter 13 and thereafter if other calculation methods are used.

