13) Discontinuation of the investigation

Reasons for discontinuation of the investigation [occurrence of adverse event (AEs), insufficient response to Humira, patient's request, no visits, others].

14) AEs (including abnormal laboratory findings)

Presence/absence and nature of AEs, date of onset, seriousness, causal relationship with Humira treatment, suspected drugs, clinical course of AEs, measures taken (measures related to Humira treatment and symptomatic treatment), outcome, laboratory findings (indicate laboratory values when abnormal laboratory findings are observed), and reasons for the rating of causal relationships when the investigator concludes that there is no causal relationship.

15) Product Quality Complaints

A Complaint is any written, electronic, or oral communication that alleges deficiencies related to the physical characteristics, identity, quality, purity, potency, durability, reliability, safety, effectiveness, or performance of a product/device after it is released for distribution.

The investigational product in this trial contains both:

-Biologic compound(s) and

-Device component(s) (pre-filled syringe, pen).

• Definition

A Product Complaint is any Complaint related to the biologic or drug component of the product or

to the medical device component(s).

For a product this may include, but is not limited to, damaged/broken product or packaging, product appearance whose color/markings do not match the labeling, labeling discrepancies/inadequacies in the labeling/instructions (example: printing illegible), missing components/product, device not working properly, or packaging issues.

For medical devices, a product complaint also includes all deaths of a patient using the device, any illness, injury, or adverse event in the proximity of the device, an adverse event that could be a result of using the device, any event needing medical or surgical intervention including hospitalization while using the device and use errors.

Any information available to help in the determination of causality by the device to the events outlined directly above should be captured.

- Reporting

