2. Definitions of terms and abbreviations

The terms and abbreviations used in this analysis plan are as follows:

Term and abbreviation	Definition
Adverse event	Any untoward or unintended symptoms (including abnormal laboratory findings), condition or illness which are not always related to Humira.
Adverse events in the safety analysis period	Adverse events which occur from the first administration date of Humira through Week 160 of administration (Day 1 + 1120). Note that if a date is not provided, it should also be included in the period for analysis.
Adverse events not in the safety analysis period	Adverse events which occur prior to the first administration date of Humira or beyond Week 160 of administration (Day 1 + 1120).
Adverse reaction	Adverse events for which the causal relation with Humira cannot be ruled out.
Adverse reactions in the safety analysis period	Adverse events which occurred in the safety analysis period and for which the causal relation with Humira cannot be ruled out.
Adverse reactions not in the safety analysis period	Adverse events which occurred not in the safety analysis period and for which the causal relation with Humira cannot be ruled out.
MedDRA/J	Medical Dictionary for Regulatory Activities / Japanese edition
SOC	System Organ Class in MedDRA/J
PT	Preferred Terms in MedDRA/J
LLT	Lowest Level Terms in MedDRA/J
CDAI	Crohn's Disease Activity Index
WPAI	Work Productivity and Activity Impairment Questionnaire : Crohn's Disease
CRP	C-reactive protein
GB	Green book. Guide on re-examination

3. Objective of this statistical analysis plan

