Analysis items: calculate the number of cases and the percentage to the number of patients in the analysis groups per type of adverse reactions (priority survey item, PT), and the number of patients with serious reactions and the percentage to the number of patients in the analysis groups regarding the adverse reactions which occurred in the safety analysis period. In addition, calculate the summary statistics (the number of patients, the mean, the minimum, the median, the maximum) for days to the onset per PT and priority survey item (for the total number of PTs) and for days from the onset date to the outcome (recovered or recovering) as well as the number of patients per outcome.

Note: When more than one identical PT is found in a patient, aggregate seriousness, days to the onset, outcome and days to the outcome (recovered or recovering) as 1 patient (case) in the following manner.

- Seriousness priority: serious > non-serious
- Days to the onset: identify the days as mentioned in “10.2 days from the first administration date of Humira to the adverse-event onset date”.
- Outcome: identify it as mentioned in “10.2 Outcome”.
- Days to outcome (recovered or recovering): identify the days as mentioned in 10.2 Days from an onset date of adverse events to the outcome confirmation date (recovered or recovering).

“2.4.1.2 A list of the onset status of adverse events (priority survey items)”

Patients for analysis: patients in the safety analysis group

Analysis objective: to show the summary statistics on the days to the onset as well as the number of patients per outcome and the days to the confirmed outcome (recovered or recovering) for adverse events of the priority survey items.

Analysis items: calculate the number of cases and the percentage to the number of patients in the analysis groups per type of adverse events (priority survey item, PT), and the number of patients with serious events and the percentage to the number of patients in the analysis groups regarding the adverse events which occurred in the safety analysis period. In addition, calculate the summary statistics (the number of patients, the mean, the minimum, the median, the maximum) for days to the onset per PT and priority survey item (for the total number of PTs) and for days from the onset date to the outcome (recovered or recovering) as well as the number of patients per outcome.

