Note: When more than one identical PT is found in a patient, aggregate seriousness, days to the onset, outcome and days to the outcome (recovered or recovering) as 1 patient (case) in the following manner.

- Seriousness priority: serious > non-serious
- Days to the onset: identify the days as mentioned in “10.2 days from the first administration date of Humira to the adverse-event onset date”.
- Outcome: identify it as mentioned in “10.2 Outcome”.
- Days to outcome (recovered or recovering): identify the days as mentioned in 10.2 Days from an onset date of adverse events to the outcome confirmation date (recovered or recovering).

“2.4.2 A list of the onset status of the priority survey items per 100 patient-year”

Patients for analysis: patients in the safety analysis group

Analysis objective: to show the onset status of the priority survey items per 100 patient-year by adverse event, serious adverse event, adverse reaction, serious adverse reaction of patients in the safety analysis group.

Analysis items: calculate the number of patients and the percentage to the number of patients in the analysis groups per type of seriousness and type of priority survey items for adverse events/reactions which occurred between the first administration date of Humira and the final administration date of Humira + 28.

In addition, calculate the number of events/reactions and the event rate per 100 patient-year.

Note: Aggregate the total number of developed events/reactions including the overlapped ones which occurred in a patient.

“2.5.1 A list of the onset status of adverse reactions with/without self-administration”

Patients for analysis: patients in the safety analysis group

Analysis objective: to show the onset status of adverse reactions with/without self-administration

Analysis item: aggregate the following items with/without self-administration for adverse reactions which occurred in the safety analysis period.

Calculate the number of patients and the percentage to the number of patients surveyed per number of patients surveyed, number of patients with adverse reactions, etc. number of adverse reactions, type of adverse reactions, etc. (SOC, PT).

“2.5.2 A list of the onset status of adverse reactions with/without self-administration”

Patients for analysis: patients excluded from the safety analysis group

Analysis objective: to show the onset status of adverse reactions with/without self-administration

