Sex, age (year), body weight (kg), BMI (kg/m²), duration of illness (year), indication (registration form), allergy history, smoking history, with smoking history (details), self-administration, tuberculosis test status, hepatitis B virus test status (registration form), complication, complication: liver disorder, complication: renal disorder, complication: blood disorder, complication: respiratory disorder, complication: diabetes mellitus, complication: osteoporosis, complication: malignant tumour, medical history, medical history: tuberculosis, medical history: non-tuberculous mycobacteriosis, medical history: interstitial pneumonia, medical history: bronchitis bacterial, medical history: aplastic anaemia, medical history: pancytopenia, medical history: malignant tumour, prior medication for Crohn's disease, prior medication: anti-TNF α drug, prior medication: aminosalicylic acid drug, prior medication: corticosteroids, prior medication: immunosuppressant, prior medication: antibiotics, prior treatment for Crohn's disease, prior treatment: surgery, prior treatment: GCAP, prior treatment: enteral nutrition therapy, prior treatment: intravenous nutrition therapy, treatment history with anti-TNF α drug for Crohn's disease, with treatment history with anti-TNF α drug for Crohn's disease, concomitant medication, concomitant medication: aminosalicylic acid drug, concomitant medication: corticosteroids, concomitant medication: immunosuppressant, concomitant medication: antibiotics, concomitant therapy for Crohn's disease, concomitant therapy: surgery, concomitant therapy: GCAP, concomitant therapy: enteral nutrition therapy, concomitant therapy: intravenous nutrition therapy, site of disease: anus/perianal region, site of disease: rectum, site of disease: stomach/duodenum, site of disease: colon, site of disease: jejunum/ileum, intestinal complication, non-intestinal complication, work condition, CDAI when the administration was started, CRP

"2.9.xx Incidence of adverse reactions per background factor and seriousness"

Patients for analysis: patients in the safety analysis group

Analysis objective: to show the onset status of non-serious/serious adverse reactions per statistically-significant background factor based on the test results in 2.9.

Analysis item: aggregate the following items per background factor and seriousness for adverse reactions which occurred in the safety analysis period.

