Calculate the number of patients and the percentage to the number of patients surveyed per number of patients surveyed, number of patients with adverse reactions, number of adverse reactions, incidence of the reactions, type of adverse events (SOC, PT).

Note: refer to the note of “2.13.1 Incidence of adverse reactions with/without hepatic function disorder and per seriousness” for serious adverse events.

“2.20 A list of the onset status of adverse reactions (all cases)”

Patients for analysis: patients in the safety analysis group

Analysis objective: to show the summary statistics on the days to the onset as well as the number of

patients per outcome and the days to the confirmed outcome (recovered or recovering) for adverse reactions.

Analysis items: calculate the number of cases and the percentage to the number of patients in the analysis groups per type of adverse reactions (SOC, PT), the number of patients with non-serious reactions and the percentage to the number of patients in the analysis groups, and the number of patients with serious reactions and the percentage to the number of patients in the analysis groups for the adverse reactions which occurred in the safety analysis period. In addition, calculate the summary statistics (the number of patients, the mean, the minimum, the median, the maximum) for days to the onset per PT, the number of patients per period from the onset date to the outcome (recovered or recovering), and the number of patients per outcome.

Note: When more than one identical PT is found in a patient, aggregate seriousness, days to the onset, outcome and days to the outcome (recovered or recovering) as 1 patient (case) in the following manner.

- Seriousness priority: serious > non-serious
- Days to the onset: identify the days as mentioned in “10.2 days from the first administration date of Humira to the adverse-event onset date”.
- Outcome: identify it as specified in 10.2 Outcomes of adverse events
- Days to outcome (recovered or recovering): identify the days as mentioned in 10.2 Days from an onset date of adverse events to the outcome confirmation date (recovered or recovering).

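### The SAP's only causality rule lets serious events alone be classed as unrelated, so non-serious events either all become adverse reactions or have no rule

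*SAP*

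**What the plan says.** SAP section 2 defines an adverse reaction as "Adverse events for which the causal relation with Humira cannot be ruled out". The definition covers any adverse event, sets no condition on seriousness and names no assessor.

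SAP section 10.2 turns this into a derived variable in the row on causal relationship of adverse events. The sentence begins "Unless a serious adverse event is assessed as" not related, continues "in the company causality assessment provided in" the AE matching list, and ends by regarding the event as having a causal relationship. Two levels follow for aggregation, with and without. The SAP gives no other causality rule.

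Several outputs in SAP section 13.2 need a causality status for non-serious events:

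- Chart 2.20 asks for "the number of patients with non-serious reactions and the percentage to the number of patients in the analysis groups".
- The 2.9.xx charts are meant "to show the onset status of non-serious/serious adverse reactions per statistically-significant background factor".
- Charts 2.13.1 to 2.16.1 split reactions by seriousness.
- Charts 2.5.1, 2.7, 2.9 and 2.17.1 report all adverse reactions.

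Protocol section 8(3)14) collects causal relationship on the CRF, together with "reasons for the rating of causal relationships when the investigator concludes that there is no causal relationship".

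**The concern.** Every adverse-reaction table depends on this one derivation, and its wording does not give the status of a non-serious event that the company rated not related. Section 2 makes that event not a reaction. The 10.2 sentence, applied to all events as its heading implies, makes it a reaction.

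Protocol section 9 lists the ADR table and ADR incidence by background factor among the safety analyses, and SAP section 3.1 says the results feed the regulatory report and the re-examination application. Two programmers could follow the SAP faithfully and deliver different non-serious and overall reaction rates.

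There is also a knock-on effect. Chart 2.9 tests adverse reactions against a long list of background factors, and a 2.9.xx chart is produced for each factor found significant. Misclassified reactions can therefore change which charts exist as well as the figures in them.

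**Working it through.** **Is there a plan figure to reproduce?** No. The documents give no event or reaction counts. The sample-size figure of about 300 does not depend on this rule.

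**Step 1: follow the rule for each kind of event.**

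| Event and company rating | Section 2 definition, taking the company rating as the judgement | 10.2 read under its row heading | 10.2 read as covering serious events only |
|---|---|---|---|
| Serious, not related | not a reaction | without | without |
| Serious, any other rating | reaction | with | with |
| Non-serious, not related | not a reaction | **with** | **no rule** |
| Non-serious, any other rating | reaction | with | **no rule** |

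The serious rows agree throughout. The non-serious rows fail on either reading.

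**Step 2: size under the first reading.** Let q be the proportion of patients with at least one non-serious event. Let r be the share of those patients who have at least one non-serious event whose relation is not ruled out.

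- Incidence of non-serious reactions by the section 2 definition: q × r
- Incidence by the literal 10.2 rule: q
- Ratio: q / (q × r) = 1/r
- Excess: q × (1 − r)

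Both inputs are assumptions: q from 20% to 60% and r from 25% to 75%.

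| q | r | q × r | Literal rule | Ratio |
|---|---|---|---|---|
| 20% | 25% | 5% | 20% | 4.0 |
| 20% | 50% | 10% | 20% | 2.0 |
| 20% | 75% | 15% | 20% | 1.33 |
| 40% | 25% | 10% | 40% | 4.0 |
| 40% | 50% | 20% | 40% | 2.0 |
| 40% | 75% | 30% | 40% | 1.33 |
| 60% | 25% | 15% | 60% | 4.0 |
| 60% | 50% | 30% | 60% | 2.0 |
| 60% | 75% | 45% | 60% | 1.33 |

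The excess runs from 20% − 15% = 5 percentage points to 60% − 15% = 45 percentage points. The ratio depends on r alone.

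For all reactions combined, the factor is at most 1/r. The rule adds at most the patients whose non-serious events were all ruled out, and the correct count being inflated is at least as large as the non-serious reaction count.

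**Step 3: size under the second reading.** The non-serious reaction count is undefined, and so is any total that includes it.

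**Step 4: what does not move.** Chart 2.4.1.2 is built "for adverse events of the priority survey items", whatever the causality. Charts 2.2 and 2.19 and the adverse-event rows of 2.4.2 also do not use the causality variable. Chart 2.4.2 reports "by adverse event, serious adverse event, adverse reaction, serious adverse reaction of patients in the safety analysis group", so only its reaction rows depend on the rule. Serious reactions are classified the same way on either reading.

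**The case against.** The best defence is that 'serious' is a stray word, perhaps from translation. The row heading covers adverse events in general, the aggregation has a without level, and section 2 does not mention seriousness. Charts 2.4.1.1 and 2.4.1.2 are planned separately for reactions and events, which would be pointless for non-serious events if every one were a reaction. A sensible programmer might apply the rule to all events without noticing the word. This is a fair reading of intent, and it shows that inflation is one possible result, not a certain one. It does not rescue the text: 10.2 is the operative rule, and neither literal reading produces what section 2 requires.

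The defence is also right that the size is illustrative, and that events misclassified as reactions can still be seen correctly in the adverse-event tables.

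A reader might go further and infer that relying on the company's rating drops events the treating physician judged related. The documents do not support that:

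- Section 2 names no assessor, so a company rating of not related is one way of ruling causality out.
- Section 10.2 also takes seriousness, outcome and onset date from company assessment, so the source is consistent.
- Nothing says how the company rating is formed or whether it may downgrade the physician's. If it never does, nothing is lost.
- Any single source gives no more reactions than a rule accepting either source. That is arithmetic, not evidence of bias.

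Nor is a rule requiring both physician and company to say not related a safe replacement. Section 10.2 admits events that did not come from the survey form. Those may have no CRF rating, and so no clear route to without.

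**Conclusion.** The rule is wrong as written for non-serious events and should be corrected. Read under its heading, it makes every non-serious event an adverse reaction and multiplies non-serious reaction incidence by 1/r: 1.33 to 4 for an assumed r of 75% to 25%, and at most that for all reactions combined. Read narrowly, it leaves those counts undefined. The conflict with section 2 is plain from the text; the size rests entirely on the assumed r, because the documents contain no event data.

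The effect is confined to outputs reporting non-serious or all adverse reactions, including the choice of 2.9.xx charts. Serious-reaction counts, adverse-event tables and the sample size are unchanged. No conclusion is drawn that company assessment suppresses physician-related events.

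**What to change.** In SAP section 10.2, delete 'serious' from the causality sentence, so that any adverse event counts as causally related unless it is assessed as not related. This brings the derivation into line with section 2 and keeps the cautious default that an event without an express not-related rating counts as related. The cost is one word.

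Before programming, confirm that the matching list carries a causality rating for non-serious events. The documents do not show its contents, and an unrated event would still default to related.

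Optional and secondary: where a physician rating exists on the CRF, print it beside the company rating in chart 1.4.1, which already lists causality. Any disagreement would then be visible without changing the derivation. This adds one column, left blank for events that have no CRF rating.
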